### **3. Statistical Analysis Plan**

This study will follow an intention-to-treat (ITT) analysis, which will include all participants randomized in the study, regardless of missing data. Our hypothesis is that children randomized to receive the Superpower Glass intervention will show a significant improvement on the primary outcome measures, as compared to controls. We will apply a mixed effects

model analysis to assess change from baseline (week 0) to post-test 1 (week 6) in the primary outcome measures.

Primary Outcome Measures:

1. Vineland Adaptive Behavior Scales, 2nd Edition (VABS-II), Socialization subscale
2. Social Responsiveness Scale 2 (SRS-2)
3. NEPSY-II, Affect Recognition subscale
4. Emotion Guessing Game (EGG) scores

Secondary Outcome Measures:

1. Brief Observation of Social Communication Change (BOSCC)
2. Vineland Adaptive Behavior Scales, 2nd edition (VABS-II) Full Scale
3. Child Behavior Checklist (CBCL)

Other measures collected:

1. Stanford-Binet Intelligence Scales, Abbreviated Battery, Fifth Edition (ABIQ)
2. Mobilized Machine Learning Autism Risk Assessment (MARA)
3. Social Communication Questionnaire (SCQ)

We will also perform sensitivity analyses to examine the extent to which outcome measures are correlated to the child's age and autism severity, as well as by usage factors, such as variation in compliance with recommended dosage and missing data from families lost to follow-up. We will use the same approach to assess differences on secondary outcomes between groups using the same mixed effects model analysis. Lastly, we will perform a six-week follow-up analysis on the treatment group to test if a return to baseline occurred.

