**c) Explain why human subjects must be used for this project.**

Human subjects must be used for this project because the purpose of the study is to determine the efficacy of this novel device in social interactions for individuals with ASD. There are no suitable animal models for facial emotion recognition in ASD, nor are there comparable behavioral therapies for animals, and therefore, human subjects must be used.

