## 2. Study Procedures:

Participants: Participants will be ages 6-12 years old. We anticipate recruiting up to 80 ASD participants. We will also be recruiting family members and friends of participants to consent to participate as "non-participants." The research staff will obtain informed consent before any study procedures begin. Consent and assent will be obtained either electronically or in-person.

For n=50 participants, we will run a cross-over design study where 25 participants will randomly be assigned to group one and continue treatment as usual (control), or group two and continue treatment as usual plus study procedures (treatment). For these 50 participants, they must receive ABA therapy in the home at least 2xs/week. We will try to understand the efficacy of the device in comparison to ABA therapy.

The procedures for the "treatment" group are as follow:

1/ complete screening questionnaires and phone screen  
2/ come in for onboarding session (as described above) and take device home to use for 6 weeks. They will use the device at least 4xs/week for 20 minute sessions with either their parents or ABA therapist.

They will have phone calls with study managers to see how usage of the device at home is going.

3/ come in for conclusion (as described above) and return device  
4/ come in 6 weeks later for follow up (as described above)

During onboarding, conclusion, and follow-up, we will also conduct unstructured interviews to get feedback from research participants. At the end of the 12 week "treatment group" period and they complete the follow up, a \$50 Amazon gift card is provided as compensation for participation in the study.

The procedures for the "control" group are as follow:

1/ complete screening questionnaires and phone screen  
2/ come in for onboarding session (as described above)  
3/ come in for an appointment (appointment 1) 6 weeks after onboarding and conduct evaluations again. Participants will now take device home to use for 6 weeks. They will use the device at least 4xs/week for 20 minute sessions with either their parents or ABA therapist.  
They will have phone calls with study managers to see how usage of the device at home is going.  
4/ come in for conclusion (as described above) and return device  
5/ come in 6 weeks later for follow up (as described above)

During onboarding, appointment 1, conclusion, and follow-up, we will also conduct

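### Four unranked primary outcomes have no stated alpha, sidedness, multiplicity control or success rule, so what counts as a positive trial can be settled after the results are seen

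*Combined protocol and SAP*

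**What the plan says.** Section 3 (Statistical Analysis Plan) puts four measures under one primary heading, numbered 1 to 4. The list starts with "Vineland Adaptive Behavior Scales, 2nd Edition (VABS-II), Socialization subscale", continues with the SRS-2 and the NEPSY-II Affect Recognition subscale, and ends with "Emotion Guessing Game (EGG) scores". The numbering is not said to be a ranking or a testing order.

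The hypothesis is that "children randomized to receive the Superpower Glass intervention will show a significant improvement on the primary outcome measures, as compared to controls". The analysis is a mixed effects "model analysis to assess change from baseline (week 0) to post-test 1 (week 6) in the primary outcome measures". For the secondary outcomes the plan says: "We will use the same approach to assess differences on secondary outcomes between groups using the same mixed effects model analysis".

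Section 1(c) states that "the purpose of the study is to determine the efficacy of this novel device in social interactions for individuals with ASD". Section 2 gives the size: "For n=50 participants, we will run a cross-over design study where 25 participants will randomly be assigned to group one", which I read as 25 per group.

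The supplied text contains no significance level, sidedness, multiplicity adjustment, lead outcome, joint test, or statement of how many primary outcomes must succeed. Some pages were not available, but Section 3 appears complete.

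**The concern.** A stated efficacy purpose and a hypothesis of significant improvement over controls are confirmatory language. They need a rule, fixed in advance, for when the claim is met. Here, a trial with one significant outcome out of four could be called positive (one measure improved) or negative (the measures as a set did not), and nothing in the plan decides between the two.

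The possible rules describe very different trials. If any one outcome is enough, the chance of a false claim exceeds the per-test level. If all four are needed, error is controlled but joint power is much lower. The plan reports neither consequence because it does not choose. Reporting all four results would help a reader see what happened, but it does not replace a rule set beforehand.

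**Working it through.** **Inputs.** From the documents: four primary outcomes; 25 per group. Assumed, because the documents give none: two-sided 0.05 per test, so 0.025 in the favourable direction; equal correlation ρ between the four test statistics, with scores aligned so that higher is better; and, for illustration only, 80% power per outcome. The plan has no error-rate or power figure to reproduce.

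**1. Any one of four counts, no true effects.** With independent tests:
- benefit only: 1 − (1 − 0.025)^4 = 1 − 0.975^4 = 0.0963
- either direction: 1 − (1 − 0.05)^4 = 1 − 0.95^4 = 0.1855

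For ρ > 0, write each statistic as √ρ·u + √(1 − ρ)·e, with u and e independent standard normals, and c = 1.96. Then

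P(at least one false benefit) = 1 − ∫ φ(u) [Φ((c − √ρ u)/√(1 − ρ))]^4 du.

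For either direction, the bracket becomes the probability that a statistic lies between −c and c. Numerical integration gives:

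| ρ | False claim of benefit | Either direction |
|---|---|---|
| 0 | 9.6% | 18.5% |
| 0.3 | 8.7% | 17.4% |
| 0.5 | 7.8% | 15.6% |
| 0.7 | 6.5% | 13.0% |
| 0.8 | 5.7% | 11.4% |
| 0.9 | 4.7% | 9.4% |
| One test alone | 2.5% | 5.0% |

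Both columns reach the single-test level only at ρ = 1. If the plan meant one-sided 0.05 per test, the false-benefit risk would be 18.5% (ρ = 0) to 8.8% (ρ = 0.9), against 5% for one test.

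**2. All four must succeed.** A false claim requires every null outcome to be significant in favour of the device. Its probability therefore cannot exceed that of a single such result, which is 2.5%. The bound is approached when three outcomes have large real effects and one has none. If no outcome has an effect, the risk is far smaller: 0.29% at ρ = 0.7 and 0.94% at ρ = 0.9.

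The cost is power. At 80% per outcome and ρ = 0, joint power is 0.80^4 = 0.41. Simulation with mean z = 2.80 gives:

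| ρ | Power, any one | Power, all four |
|---|---|---|
| 0 | 99.8% | 41.0% |
| 0.3 | 98.5% | 49.8% |
| 0.5 | 96.7% | 55.5% |
| 0.7 | 93.7% | 62.0% |

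**3. Holm at overall two-sided 0.05.** The smallest p-value is compared with 0.05/4 = 0.0125. If there are no true effects, simulated either-direction error is 4.9% (ρ = 0), 3.7% (0.7) and 2.6% (0.9). At ρ = 0, the chance of a favourable result passing that first step is 1 − (1 − 0.00625)^4 = 0.0248, close to the 2.5% of a single test.

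Detectable effect at 80% power, from the noncentral t with 25 per group and 48 degrees of freedom (unadjusted week-6 comparison, no dropout): 0.809 SD at 0.05 and 0.976 SD at 0.0125. The ratio is 0.976/0.809 = 1.21.

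An outcome with 80% power at 0.05 keeps 72.7% (ρ = 0) to 70.2% (ρ = 0.7) under Holm if all four effects are real and equal. It keeps 62.0% if it is the only real effect.

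**The case against.** The strongest reply is that the hypothesis most naturally means improvement across all the listed measures. On that reading, error is controlled with no adjustment. This stands as a possible reading, and the fix must allow for it. But Section 3 never says that all four are required, and nothing suggests that the study was sized with the joint power of that rule in mind.

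A reader might go further the other way and infer that the plan carries a false-positive risk of about 19%. The documents do not support that. The figure needs an any-one rule that the plan does not state, an alpha that it does not give, and zero correlation. At two-sided 0.05 it also counts results showing the device to be worse, which could not make this trial positive. The matching figure for benefit is about half as large.

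It is also fair that the outcomes, time point and type of model are named in advance, which limits selection. That does not settle how many outcomes must succeed. Correlation between the outcomes softens the any-one inflation, but even at 0.9 the risk is nearly double that of a single test.

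**Conclusion.** The concern holds as an undefined decision rule, not as a demonstrated inflation of error. As written, four unadjusted tests could let a single significant result support the efficacy claim, and the plan neither adopts nor excludes that use. The choice of rule moves the risk of falsely claiming benefit between at most 2.5% (all four) and 4.7% to 9.6% (any one). With 80% power per outcome, it moves the chance of a positive trial between 41–62% (all four) and about 94–100% (any one) for correlations of 0 to 0.7.

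The sizes rest on the assumed two-sided 0.05, equal correlations and hypothetical 80% power. The absence of a rule rests on the text alone and depends on none of them. The remedy is cheap, but it is credible only if made before the results are seen.

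**What to change.** Add to Section 3:

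> Each primary outcome is analysed in its own mixed effects model; the test is the between-group difference in change from week 0 to week 6. The four tests use the Holm procedure at overall two-sided alpha 0.05. The trial is positive if at least one primary outcome has a Holm-adjusted p of 0.05 or less with the effect favouring the device, and efficacy is claimed only for the outcomes that meet this; otherwise the trial is not positive.

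Holm is suggested because the plan ranks none of the four. If the sponsor intends all four to be required, state that rule and its lower joint power instead. A single pre-specified primary outcome or a fixed testing order would also close the gap.

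The cost is one paragraph, with no new data, visits or participants. The price of Holm is statistical: a detectable effect of about 0.98 SD rather than 0.81 SD at the first step, and per-outcome power of about 70–73% (all four effects real) or 62% (only one real) where it would have been 80% unadjusted.

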unstructured interviews to get feedback from research participants. At the end of the 18 week "control group" period and they complete the follow up, we will provide to them a \$50 Amazon gift card.

Screening Questionnaire: We will send around a link to a redcap survey for all recruited participants from the recruitment website and with other recruitment efforts. We will ask interested participants to fill out the Screening Questionnaire. Our goal will be to determine eligibility based on location (needs to be local to Stanford), still interested in participating, has a child that meets our eligibility criteria, and a brief overview of the child. Eligible families will be contacted via email or phone to set up scheduling for in-lab study sessions. Parents will be asked to fill out these questionnaires no more than 4 times each (Baseline, at the end of the intervention, and at 6-weeks follow-up).

Standardized Behavioral and Clinical Characterization Scales, Checklists, and Measures:

*Clinical Phenotyping Measures Parents:* The Social Responsiveness Scale (SRS-2), The Vineland Adaptive Behavior Scale (VABS-2), Social Communication Questionnaire (SCQ), and Child Behavior Checklist (CBCL).

*Child:* Participants will also undergo the Abbreviated Battery IQ (ABIQ), which consists of two subsections of the Stanford-Binet, 5th Edition Intelligence Test. We will also collect the NEPSY-II Affect Recognition and Emotion Guessing Game, as well as Overall Social Interaction (Brief Observation of Social Communication Change, BOSCC). At one of the in-person appointments, we will have participants and consented/assented family members read aloud a script (see section 16) into a microphone to collect audio data to later analyze to help with expression recognition software.

Study Procedures:

First session (Onboarding): Subjects and family members will be asked to come to the [name] Lab at [name] to obtain written or electronic consent. Individuals will meet the study team, will discuss expectations with study manager, discuss how to use the device units, and go over scheduling. Cognitive testing will be conducted in a private assessment where participants will complete the ABIQ. The child/family will then take the Glass home for the duration of the study or we will mail the units home.

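### The SAP does not say how the baseline score enters the week-0 to week-6 model; a raw-change fit would lose precision for outcomes whose slope on baseline is clearly below 1

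*Combined protocol and SAP*

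**What the plan says.** The primary model is given in one sentence of section 3 (Statistical Analysis Plan): a mixed effects "model analysis to assess change from baseline (week 0) to post-test 1 (week 6) in the primary outcome measures". The hypothesis is a between-arm one: treated children "will show a significant improvement on the primary outcome measures, as compared to controls". For the rest, section 3 says: "We will use the same approach to assess differences on secondary outcomes between groups using the same mixed effects model analysis". It lists no fixed effects, covariates, random effects, covariance structure or constraint on the baseline means. Age and autism severity appear only in sensitivity analyses, which also cover "missing data from families lost to follow-up".

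Section 2 (Study Procedures) gives the size: "For n=50 participants, we will run a cross-over design study where 25 participants will randomly be assigned to group one". I read this as 25 per arm. The controls "come in for an appointment (appointment 1) 6 weeks after onboarding and conduct evaluations again", before they receive the device, and the treated children return after six weeks of use. The analysis therefore rests on two scores per child, at week 0 and week 6.

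Neither section states a correlation between the two visits, an SD, an effect size, an alpha level or a power.

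**The concern.** The sentence in section 3 fits at least two different analyses. In one, change is the response, or arm and time interact with a baseline mean estimated freely in each arm. With complete data on two visits, both of these reduce to comparing mean raw change. In the other, the arms are compared at week 6 given the baseline score, either as a covariate or by giving both arms one baseline mean.

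Both estimate the same effect without bias over randomisations, but their precision differs. Raw change subtracts the whole baseline score, as if the slope of week 6 on baseline were 1. When the true slope is clearly lower, the subtraction adds noise. Chance baseline imbalance is the source of that noise and should not be counted as a second harm.

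With about 25 children per arm, one unstated modelling choice could cost as much as several children per arm on some outcomes. Because section 3 carries the model over, the gap affects all four primary and three secondary outcomes.

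**Working it through.** The plan has no power or sample-size figure to reproduce.

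**Inputs.** From section 2: N = 50, read as 25 per arm. Assumed, because the documents are silent: correlation r between week 0 and week 6; k = week-6 SD divided by baseline SD; baseline SD set to 1; for power, an effect of 0.5 SD and a two-sided 5% test. The within-arm slope is b = rk.

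**Formulas.**
- Raw change: variance proportional to 1 + k² − 2rk.
- Baseline-adjusted: k²(1 − r²) × (N − 3)/(N − 4). The last factor is the price of estimating the slope, 47/46 = 1.022.
- Before that price, the saving is (1 + k² − 2rk) − k²(1 − r²) = (1 − b)². It is zero only at b = 1.

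**Equal SDs (k = 1).** The ratio of adjusted to raw variance is (1 + r)/2 × 47/46. At r = 0.5 this is 0.75 × 1.022 = 0.766. Power is from the noncentral t distribution (48 and 47 df). The last column is 25 divided by the ratio: the number per arm that raw change would need for the same precision.

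| r | variance ratio | power, raw | power, adjusted | equivalent n per arm |
|---|---|---|---|---|
| 0.5 | 0.77 | 41% | 51% | 33 |
| 0.7 | 0.87 | 61% | 67% | 29 |
| 0.8 | 0.92 | 78% | 81% | 27 |
| 0.9 | 0.97 | 97% | 98% | 26 |

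Simulation of 20,000 trials per value gave ratios of 0.773, 0.866 and 0.970 at r = 0.5, 0.7 and 0.9.

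**Break-even.** Adjustment gains when (1 − b)² exceeds (k² − b²)/46. At k = 1 this reduces to 46(1 − b) = 1 + b, so b = 45/47 = 0.957. The point moves with k. At k = 1.2 it is near b = 0.88, where (0.12)² = 0.0144 and (1.44 − 0.7744)/46 = 0.0145.

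**Unequal SDs**, variance ratio:

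| k | r = 0.5 | 0.7 | 0.8 | 0.9 |
|---|---|---|---|---|
| 0.9 | 0.68 | 0.77 | 0.81 | 0.83 |
| 1.1 | 0.84 | 0.94 | 0.99 | 1.02 |
| 1.2 | 0.89 | 0.99 | 1.02 | 1.00 |

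Over k from 0.8 to 1.2 and r from 0.30 to 0.95, the worst loss is 2.2%, at b = 1.

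**Missing week-6 scores.** With 4 of 25 missing at random per arm (assumed) and k = 1, I compared likelihood fits with common and free baseline means in 60,000 simulated trials per value. The ratios were 0.79, 0.89, 0.94 and 0.98 at r = 0.5, 0.7, 0.8 and 0.9. Power went from 36% to 44%, 54% to 59%, 71% to 74% and 94% to 95%.

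**Equivalence check.** In one simulated complete data set (r = 0.6), the arm-by-time mixed model with free baseline means gave 0.526 (SE 0.258), identical to raw change. A random-intercept model with a common baseline mean gave 0.533 (SE 0.231). The covariate model gave 0.533 (SE 0.237).

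**The case against.** The strongest reply is that the plan may already intend an adjusted model. The wording does not exclude it, and if so nothing is lost. This stands: the defect is an unspecified model, and an inferior choice has not been shown. A reader might infer that the plan ignores baseline. The text does not support that, because baseline is the reference point for change and a mixed model may also carry it as a response.

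The reply also says that the benefit depends on an unknown correlation and SD ratio, and is small when scores are stable. That stands too. With equal SDs the gain is useful up to r of about 0.7, modest at 0.8 and negligible at 0.9.

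Three stronger readings are tempting and fail:
- *Adjustment wins whenever the slope is below 1.* Not at N = 50. At k = 1.1 and r = 0.9 the slope is 0.99 and the ratio is 1.02. Slopes well above 1, on the other hand, also favour adjustment.
- *Raw change is biased by chance imbalance.* It is not. In simulated complete-data trials both estimators averaged 0.50 for a true effect of 0.5.
- *The covariate form guards against baseline being scored after the family knows its arm.* Section 2 leaves that order open: treated families "come in for onboarding session (as described above) and take device home to use for 6 weeks" within their own group's sequence. But with complete data the covariate and common-baseline models give the same estimate; over 4,000 simulated trials the largest difference was below 1e-7. If a systematic 0.2 SD baseline difference persisted to week 6, adjustment would be biased by +0.10 to +0.02 at r = 0.5 to 0.9, and raw change by nothing. The order of scoring and allocation is a separate point, and choosing between the two adjusted forms does not settle it.

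A common-mean model also needs care with its standard errors. In the same 4,000 trials (r = 0.6), uncorrected REML gave a type I error of 6.2% with a z test and 5.8% with t on 48 df, against 5.4% for the covariate model (Monte Carlo SE about 0.35%).

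**Conclusion.** The point holds as a cheap improvement in precision that should be made; it is not a claim of bias. Its size is conditional on a raw-change or free-baseline fit. With equal SDs, the variance reduction then runs from about 23% at r = 0.5 to 3% at r = 0.9. It is larger if the spread narrows by week 6 and smaller if it widens modestly. The power figures rest further on an assumed 0.5 SD effect. No correlation or SD in the documents says where any of the seven outcomes falls in this range, so confidence in the practical gain is medium.

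**What to change.** Add to section 3 a statement such as: *For each primary and secondary outcome, the arms will be compared at week 6 with adjustment for that outcome's own week-0 score.* Then name one form in advance:

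- the week-0 score as a covariate, which is the simpler; or
- a mixed model fitted by REML, with both scores as responses, one baseline mean common to both arms, unstructured covariance, small-sample degrees of freedom, and the week-6 arm difference as the treatment effect. This keeps children who have only one of the two scores, which suits the plan's intention-to-treat statement.

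If a model of this kind is already intended, the same sentence records it and closes the choice before data are seen.

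No new data or visits are needed. The statistical cost is the factor 47/46, about 2% in variance, already included in every ratio above except the simulated missing-data ones, where it arises directly. Where the slope is close to 1 there is no gain to offset it.

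### The only analysis after the device is returned tests for a return to baseline in the treatment arm alone, with no interval, margin or reading rule; it cannot establish a return or separate kept benefit from drift

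*Combined protocol and SAP*

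**What the plan says.** Section 3 sets the mixed model to "assess change from baseline (week 0) to post-test 1 (week 6) in the primary outcome measures". Its hypothesis is that treated children "will show a significant improvement on the primary outcome measures, as compared to controls". Secondary outcomes get the same approach, with no later time point named. The closing sentence of the section is the only plan for what happens off device: "we will perform a six-week follow-up analysis on the treatment group to test if a return to baseline occurred". It names no outcome, model, interval, margin or rule of interpretation.

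Section 2 (Study Procedures) describes the design: "For n=50 participants, we will run a cross-over design study where 25 participants will randomly be assigned to group one". The treatment arm uses the device in weeks 0 to 6 and then must "4/ come in 6 weeks later for follow up (as described above", which is week 12. The control arm must "3/ come in for an appointment (appointment 1) 6 weeks after onboarding and conduct evaluations again", then takes the device home for six weeks. Its next step, "4/ come in for conclusion (as described above) and return device", therefore also falls at week 12. Its own follow-up is at week 18 ("At the end of the 18 week 'control group' period and they complete the follow up").

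**The concern.** Whether a return occurred is a question about the absence of a difference. The word test, with no margin, points to a difference test, which can argue against a return but never show one. Because the plan gives no reading rule, a non-significant result could be reported as a return when a moderate gain has been kept.

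The opposite error is also open. The analysis is confined to one arm, so anything that moves scores in all the children over 12 weeks (ageing, retest gains, continuing ABA therapy) counts as retained benefit. The control arm is seen at week 12 too, but no stated analysis uses that visit or the week-18 one. At stake is the trial's only statement about durability.

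**Working it through.** **Inputs.** From the documents: 50 randomised, read as 25 per arm (Section 2); treatment visits at weeks 0, 6 and 12; control visits at weeks 0, 6, 12 and 18. The 50 comes with no alpha, power, effect size or SD, so there is no figure of the plan's own to reproduce. Assumed: two-sided alpha 0.05; 20 completers per arm as the lower case; correlation r between visits from 0.3 to 0.9; drift of 0.2 or 0.3 SD. All results are in SDs of the within-child paired difference.

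**1. Difference test, week 12 against week 0, treatment arm.** Paired t-test; power = P(|T| > t(0.975, n−1)), where T is non-central t with n−1 degrees of freedom and non-centrality d√n. For n = 25 and d = 0.3 the non-centrality is 0.3 × 5 = 1.5 against a critical value of 2.064.

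| True retained gain (SD) | Missed, n = 25 | Missed, n = 20 |
|---|---|---|
| 0.3 | 69.8% | 75.3% |
| 0.4 | 51.6% | 60.3% |
| 0.5 | 33.0% | 43.5% |
| 0.8 | 3.0% | 7.6% |

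A large retained gain would be seen; a moderate one often would not. The 95% interval half-width is t(0.975, n−1)/√n: 2.064/5 = 0.41 SD at n = 25, and 0.47 SD at n = 20.

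**2. Would an equivalence test rescue it?** Two one-sided 5% tests, true change zero. Approximate margin for 80% power at n = 25: (1.645 + 1.282)/5 = 0.585 SD. Simulation with the t distribution gives 0.60 SD (0.68 SD at n = 20). At a margin of 0.3 SD, power with 25 children is 2%. A formal claim of return is therefore possible only with a wide margin.

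**3. Drift.** Suppose no gain is retained and the only change is common drift. The test in step 1 is then significant in 16.1% of trials at 0.2 SD and 30.2% at 0.3 SD (n = 25), against the nominal 5%.

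**4. What the week-12 control visit adds.** Write eff for the change at end of device and ret for the change kept six weeks later, with T for treatment and C for control. Common drift cancels between arms:

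- Week-6 arm difference: eff_T.
- Week-12 arm difference: ret_T − eff_C = (ret_T − eff_T) + (eff_T − eff_C).
- Sum of the two: ret_T + (eff_T − eff_C).

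If the device effect is the same for a week-0 and a week-6 start, the last bracket is zero. The week-12 difference then estimates loss since end of device, and the sum estimates retained gain over baseline.

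**5. Precision of these contrasts.** Equal correlation r between visits, baseline-adjusted, 25 per arm, t(0.975, 47) = 2.012:

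- Week-12 difference: 2.012 × √[(2/25)(1+r)/2]. At r = 0.3 this is 2.012 × √0.052 = 0.46; at r = 0.9, 2.012 × √0.076 = 0.55.
- Sum: 2.012 × √[(2/25)(1+2r)]. At r = 0.3 this is 2.012 × √0.128 = 0.72; at r = 0.9, 2.012 × √0.224 = 0.95.

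With 20 per arm the ranges are 0.52 to 0.62 and 0.81 to 1.07. If correlation instead decays with time (AR(1), 0.3 to 0.9, normal quantile, 25 per arm), they are 0.47 to 0.73 per SD of the week 6 to 12 change, and 0.64 to 0.84 per SD of the week 0 to 12 change.

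Tested against zero under equal correlation, the sum misses a 0.5 SD retained gain in 72% to 82% of trials and detects 0.8 SD in 38% to 59%.

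**The case against.** Several stronger readings are tempting, and the documents do not support them.

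- *That the plan names no contrast at all.* Section 3 defines baseline as week 0, and the follow-up visit is week 12 for this arm, so the comparison is implied. What is missing is the interval, the margin and the reading rule.
- *That the sponsor will read non-significance as a return.* The plan does not say so, and significance is mentioned only in the hypothesis on the primary outcomes. The plan leaves the reading open; it does not commit to it.
- *That the trouble is the 25 children.* A difference test cannot prove equality at any size. The small arm only makes misses more frequent.
- *That the randomised contrasts should replace the within-child ones.* The week-12 arm difference answers another question, loss since end of device. It is zero under full retention and also zero if the device never worked. The sum does address return to baseline, but with a half-width of 0.72 to 0.95 SD against 0.41 SD for the within-child change. Both rest on equal device effects from either start, which these visits cannot check, and there is no untreated group at week 12. Relegating the within-child changes to description would exchange possible drift bias for a large loss of precision.

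Feasibility is also less than certain. In Section 2, the sentence on repeat questionnaires follows the screening text, so it is unclear which scales it covers. The Conclusion paragraph mentions only interviews and feedback, and the emotion recognition test is tied to check-ins.

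These objections limit the fix. They do not supply the missing interval or rule, or a use for the control arm after week 6.

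**Conclusion.** The concern holds in a limited form. As written, the follow-up analysis cannot establish a return, will often miss a moderate retained gain, and cannot tell such a gain from common drift. Its size depends on the assumed alpha, completers and drift in steps 1 and 3, since the documents state none of them. The scheduled visits allow a drift-free check, but an imprecise one that depends on equal device effects, so it belongs beside the within-child estimates and not in their place. The randomised comparison over weeks 0 to 6 is not touched. This is a change the sponsor should make, but not one on which the trial's main result depends.

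**What to change.** Replace the closing sentence of Section 3 with text such as:

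> For each outcome measured at follow-up, the mixed model will be extended beyond week 6 to estimate the treatment-arm change from week 0 to week 12 and from week 6 to week 12, with 95% confidence intervals. These changes include common drift. Neither return to baseline nor retention will be concluded from a non-significant test. The baseline-adjusted week-12 difference between randomised arms (treatment six weeks off device, control at end of device) will also be reported with a 95% confidence interval. It estimates loss since end of device free of common drift, will be read together with the week-6 effect, and assumes the same device effect for a week-0 and a week-6 start. The sum of the week-6 and week-12 arm differences is a sensitivity estimate of retained gain over baseline. The control arm's own follow-up changes (weeks 6, 12 and 18) will be reported alongside.

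Also list which outcomes are measured at each arm's week-12 visit. The arm contrast can be used only for those, and this is least clear for the two child tests among the primary outcomes (NEPSY-II Affect Recognition and the Emotion Guessing Game).

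The cost is some SAP text and a little more analysis, with no new visits provided the outcomes are already collected at those times. The price in interpretation is that the drift-free estimates will often be inconclusive. If the device effect differs between the two start times, both shift by that difference.
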